### 3.2 Clinical Experience with CO-1686

CO-1686 has been evaluated in Study CO-1686-008, an ongoing first-in-human Phase 1/2 study in patients with advanced NSCLC and 1 completed Phase 1 study in healthy volunteers (CO-1686-016).

### 3.2.1 Safety

#### Study CO-1686-008

CO-1686-008 is a 2-part, open-label, safety, pharmacokinetic (PK), and preliminary efficacy study of CO-1686 in patients with advanced/metastatic NSCLC. As of 04 June 2014, 148 patients with advanced/metastatic NSCLC have received at least 1 dose of CO-1686. In the initial stage of the study, 57 patients were treated with CO-1686 administered as free base capsules at doses ranging from 150 mg up to 1800 mg daily. Subsequently, CO-1686 HBr tablets were introduced into the study to be used in the later dose escalation cohorts. Ninety-one patients have been treated with CO-1686 administered as HBr tablets at doses of 500 mg twice daily (BID) (n = 18), 625 mg BID (n = 17), 750 mg BID (n = 50) and 1000 mg BID (n = 6). At the time of this summary, preliminary safety data are available in the clinical database for 148 patients.

**Dose-limiting Toxicities (DLTs):** Enrollment of patients to the dose escalation phase was completed in February 2014 with a DLT rate of < 33% at all evaluated doses. The DLT evaluable population included all patients who have completed Cycle 1 and who were enrolled while the dose escalation part of the study was ongoing. The most frequently reported DLT was hyperglycemia/glucose tolerance impaired which occurred at a similar frequency (10% to 20%) across all CO-1686 HBr dose levels (500 mg BID, 625 mg BID, 750 mg BID, 1000 mg BID). Hyperglycemia has been effectively managed with the addition of anti-hyperglycemic therapy and/or dose reductions. Guidance for the management of hyperglycemia associated with CO-1686 treatment is provided in Section 7.4.1.

**Serious Adverse Events (SAEs)**: A total of 43 patients experienced at least 1 SAE and 17 patients reported an SAE assessed as related to study drug. Treatment-related SAEs are summarized in Table 3-1. There were 11 deaths while on study or within 28 days after last dose. Eight deaths were due to progression of NSCLC, 1 due to pneumonia, 1 due to pulmonary embolism, and 1 of unknown cause, with all assessed as not related to study drug.

Table 3-1: Treatment-related SAEs Reported in any Patient in Study CO-1686-008

Daily Dose	< 1800 mg	1800 mg	1000 mg	1250 mg	1500 mg	2000 mg	Overall
	(N=38)	(N=19)	(N = 18)	(N = 17)	(N=50)	(N=6)	(N = 148)
Formulation	FB	FB	HBr	HBr	HBr	HBr	
Frequency	Variousa	900 mg BID	500 mg BID	625 mg BID	750 mg BID	1000 mg BID	
Overall	4 (10.5%)	1 (5.3%)	4 (22.2%)	3 (17.6%)	4 (8.0%)	1 (16.7%)	17 (11.5%)
Cardiac Disorders							_
Pericarditis	1 (2.6%)	0	0	0	0	0	1 (0.7%)
Gastrointestinal Disorde	ers	1	1	1			1
Diarrhea	1 (2.6%)	1 (5.3%)	0	0	0	0	2 (1.4%)
Nausea	1 (2.6%)	0	1 (5.6%)	0	1 (2.0%)	0	3 (2.0%)
Pancreatitis	0	0	1 (5.6%)	0	0	0	1 (0.7%)
Vomiting	2 (5.3%)	0	1 (5.6%)	0	1 (2.0%)	0	4 (2.7%)
Infections and Infestation	ons	1	1	1			1
Gastroenteritis	0	0	0	0	1 (2.0%)	0	1 (0.7%)
Investigations							_
ECG QT prolonged	0	0	0	1 (5.9%)	1 (2.0%)	0	2 (1.4%)
ECG T wave inversion	0	0	0	0	1 (2.0%)	0	1 (0.7%)
Transaminases increased	0	1 (5.3%)	0	0	0	0	1 (0.7%)
Metabolism and Nutrition	on Disorders	1	1	1			1
Decreased appetite	0	1 (5.3%)	0	0	0	0	1 (0.7%)
Combined terms of hyperglycemia	1 (2.6%)	0	4 (22.2%)	1 (5.9%)	2 (4.0%)	1 (16.7%)	9 (6.1%)
Hypoglycemia	1 (2.6%)	0	0	0	0	0	1 (0.7%)
Hypokalemia	0	0	0	1 (5.9%)	0	0	1 (0.7%)
Respiratory, Thoracic a	nd Mediastinal D	Disorders	1	1	 		•
Pneumonitis	0	0	0	1 (5.9%)	0	0	1 (0.7%)
		1	I	I	l l		

**Abbreviations:** FB = free base

<sup>a 150 mg to 900 mg daily (QD), 100 mg to 600 mg twice daily (BID), 400 mg 3 times a day (TID)

**Treatment-related Adverse Events (AEs):** Treatment-related AEs reported in at least 5% of patients summarized in Table 3-2.

The most frequently reported treatment-related AEs (all grades) were nausea (28.4%), and hyperglycemia/glucose tolerance impaired (33.1%). The majority of AEs are mild or moderate. The most frequently reported Grade 3 or higher AE, occurring in 18.5% of patients overall, was hyperglycemia/glucose tolerance impaired.

As expected due to CO-1686 selectivity for mutant EGFR, dose related WT-driven rash and diarrhea has not been observed. All reported events of diarrhea were either Grade 1 or Grade 2.

The most common skin reaction reported in patients treated with EGFR-TKIs is a follicular acneiform eruption. In Study CO-1686-008, rash, irrespective of causality, was reported infrequently (overall 7 patients; 5.4%) and events were mild. Only 1 event of dermatitis acneiform and 1 event of follicular rash have been reported.

There has been 1 AE and 1 SAE of pneumonitis. Both events were assessed as related to CO-1686. Both cases resolved when CO-1686 treatment was stopped.

**Electrocardiograms (ECGs):** ECG results are available for 122 patients. CO-1686 causes an increase in the QTc interval of the ECG, with onset between Day 1 and 15 of treatment. Overall, 9 patients (7.4%) have experienced a QT interval corrected using Fridericia's method (QTcF) > 500 ms.

Prolonged QTc is managed effectively by dose reduction, and all CO-1686 protocols contain patient selection criteria and specific guidance for the management of patients who develop prolonged QTc.

In summary, CO-1686 has a manageable safety profile at all doses evaluated.

Table 3-2: Treatment-related AEs Reported in at Least 5% of Patients or Treatment-related Events Associated with Inhibition of WT EGFR in Study CO-1686-008

Total Daily Dose	< 1800 mg	1800 mg a	1000 mg	1250 mg	1500 mg	2000 mg	Total
	(N = 38)	(N=19)	(N=18)	(N = 17)	(N=50)	(N=6)	(N = 148)
Formulation	FB	FB	HBr	HBr	HBr	HBr	
Frequency	Various b	900 mg BID	500 mg BID	625 mg BID	750 mg BID	1000 mg BID	
Overall n of patients with at least 1 TEAE	28 (73.7%)	18 (94.7%)	16 (88.9%)	15 (88.2%)	28 (56.0%)	6 (100.0%)	111 (75.0%)
Gastrointestinal Disorders				1		1	
Diarrhea	6 (15.8%)	6 (31.6%)	4 (22.2%)	4 (23.5%)	6 (12.0%)	2 (33.3%)	28 (18.9%)
Nausea	8 (21.1%)	6 (31.6%)	6 (33.3%)	7 (41.2%)	12 (24.0%)	3 (50.0%)	42 (28.4%)
Vomiting	5 (13.2%)	2 (10.5%)	3 (16.7%)	4 (23.5%)	4 (8.0%)	0	18 (12.2%)
General Disorders and Admi	nistrative Site C	Conditions					
Fatigue	9 (23.7%)	6 (31.6%)	5 (27.8%)	3 (17.6%)	5 (10.0%)	1 (16.7%)	29 (19.6%)
Investigations	1				1	1	
ECG QT prolonged	0	2 (10.5%)	0	2 (11.8%)	5 (10.0%)	3 (50.0%)	12 (8.1%)
Metabolism and Nutrition Di	sorders				1	1	
Glucose tolerance impaired/elevated glucose/hyperglycemia	4 (10.5%)	6 (31.6%)	11 (61.1%)	10 (58.8%)	14 (28.0%)	4 (66.7%)	49 (33.1%)
Decreased appetite	1 (2.6%)	6 (31.6%)	4 (22.2%)	3 (17.6%)	2 (4.0%)	2 (33.3%)	18 (12.2%)
Musculoskeletal and Connect	tive Tissue Disor	rders			1	1	
Muscle spasms	3 (7.9%)	4 (21.1%)	3 (16.7%)	0	3 (6.0%)	0	13 (8.8%)
Myalgia	3 (7.9%)	4 (21.1%)	2 (11.1%)	0	1 (2.0%)	1 (16.7%)	11 (7.4%)
Skin and Subcutaneous Tissu	e Disorders			•		.                                      	
Combined term for rash	0	0	1 (5.6%)	0	0	1 (16.7%)	2 (1.4%)

<sup>a 10 patients transitioned to 500 mg BID HBr on availability

 $^{\rm b}$  - 150 mg to 900 mg QD, 100 mg to 600 mg BID, 400 mg TID

#### Study CO-1686-016

CO-1686-016 was a 3-part study in healthy male subjects which investigated the PK and safety of single and short course repeat doses of CO-1686 HBr salt. In this study, CO-1686 HBr was administered at single doses up to 1000 mg in the fasted state and at 500 mg BID in the fed state without significant adverse effects. Following CO-1686 HBr dosing over 4 days at 500 mg BID in a fed state, 3 of 6 healthy male subjects were noted to show asymptomatic increase in QTc on Day 4 of dosing which resolved when CO-1686 was discontinued.

#### 3.2.2 Activity of CO-1686

CO-1686-008 is a 2-part, open-label, safety, PK, and preliminary efficacy study of CO-1686 in patients with advanced NSCLC. The dose escalation phase of the study has been completed.

Although the primary objectives of Phase 1 of study CO-1686-008 were to evaluate the safety, toxicity and PK profile of CO-1686, encouraging signals of activity have been observed in an EGFR mutation positive patient population previously treated with 1 of more lines of an EGFR-TKI (e.g., erlotinib, gefitinib, afatinib) and chemotherapy.

Response Evaluation Criteria in Solid Tumors (RECIST) response data are available for 40 patients with centrally confirmed T790M+ disease and are summarized in Table 3-3. The current objective response rate (ORR) is 55% and the disease control rate (DCR) is 93%. Median PFS has not been reached, but currently exceeds 12 months, and is shown in Figure 3-4. In patients with T790M negative disease, activity is more modest with a current median PFS of 169 days (Figure 3-4).

[figure not shown]
Table 3-3: Best Response, Objective Response, and Disease Control Rate in T790M+ Patients

	900 mg BID FB (N = 8)	500 mg BID HBr (N = 6)	625 mg BID HBr (N = 9)	750 mg BID HBr (N = 13)	1000 mg BID HBr (N = 4)	Overall (N = 40)
Best Response a	(14 – 8)	(14 – 0)	(14 – 9)	(14 – 13)	(14 – 4)	
PR	6 (75.0%)	3 (50.0%)	5 (55.6%)	5 (15.2%)	3 (75.0%)	22 (36.7%)
SD	2 (25.0%)	2 (33.3%)	2 (22.2%)	8 (24.2%)	1 (25.0%)	15 (25.0%)
PD	0 (0.0%)	1 (16.7%)	2 (22.2%)	0 (0.0%)	0 (0.0%)	3 (5.0%)
End of Cycle 2 scan not yet reached	0 (0.0%)	0 (0.0%)	0 (0.0%)	20 (60.6%)	0 (0.0%)	20 (33.3%)
Objective Response a, b	6 (75.0%)	3 (50.0%)	5 (55.6%)	5 (38.5%)	3 (75.0%)	22 (55.0%)
(CR, PR)						
Disease Control Rate a, b	8 (100.0%)	5 (83.3%)	7 (77.8%)	13 (100.0%)	4 (100.0%)	37 (92.5%)
(CR, PR, SD)						

<sup>a Data shown are for patients with measurable disease at baseline

b Percentage based on patients with non-missing best response

Figure 3-4: Kaplan-Meier Curves of Progression-free Survival by T790M Status for 900 mg BID Free Base and All HBr Patients

## 3.2.3 Pharmacokinetics of CO-1686 HBr

### Study CO-1686-016

In healthy volunteers (Study CO-1686-016), maximum concentration ( $C_{max}$ ) and area under the curve from time zero to 24 hours ( $AUC_{0-24}$ ) of CO-1686 increased with ascending single doses of the CO-1686 HBr formulation (50 mg to 1000 mg), with CO-1686 plasma levels increasing in a less than dose proportional manner above 125 mg.

[figure not shown]
The single dose PK of CO-1686 HBr was compared in the fasted and fed state, and it was concluded that a high-fat meal increased the plasma drug concentrations from 3 to 12 hours postdose with a mean increase of 172% at 12 hours postdose ( $C_{12h}$ : -22% to +400%) and a mean increase of 77% in AUC0-24 (+10% to 146%) with no change in elimination half-life ( $T_{1/2}$ ); a slight mean increase of 12% in  $C_{max}$  was observed and a delayed time to maximum concentration ( $T_{max}$ ) was seen in a majority of subjects.

Six healthy subjects were dosed, in the fed state, with 500 mg BID CO-1686 HBr for 4 days. PK profiles of CO-1686 following morning and evening dosing were similar, with low intra-subject variability (Day 1 and Day 4 comparison). There was no accumulation of CO-1686.

### Study CO-1686-008

In the patient study (CO-1686-008), PK following HBr salt administration were available from a total of 44 patients (4 started at 500 mg BID, 10 switched from CO-1686 free base to 500 mg BID HBr, 15 started at 625 mg BID, 9 started at 750 mg BID, and 6 started at 1000 mg BID). CO-1686 HBr showed increased absorption and thus, higher exposure than free base. The median  $T_{max}$  was 2 to 3.25 hrs and  $T_{1/2}$  ranged from 1.7 to 4.7 hrs. Following CO-1686 HBr administration, exposure (measured as  $C_{max}$  and  $AUC_{0-24}$ ) increased dose-proportionally from 500 mg to 1000 mg BID (Figure 3-5).

Figure 3-5: Individual CO-1686 AUC0-24 on Day 1 Following 500 mg to 1000 mg CO-1686 HBr BID

# 3.3 Rationale for Study

NSCLC patients whose tumors have mutations in the EGFR gene experience improved clinical outcomes with EGFR-targeted therapy as compared to chemotherapy. Clinical improvements notwithstanding, patients receiving EGFR-directed therapy experience significant skin rash and diarrhea related to inhibition of the WT EGFR in skin and intestine, respectively.  While efficacy is improved with EGFR-TKIs relative to chemotherapy, median PFS is only in the 10-month range. New therapies that provide longer PFS and provide a tolerable side effect profile are needed.

CO-1686 effectively targets both the most common activating EGFR mutations and the most common mutation driving EGFR resistance, T790M, but spares the WT EGFR receptor. The hypothesis is that CO-1686 will drive more durable disease control in the first-line setting, through inhibition of the activating mutations and suppression of T790M development, with improved tolerability owing to lack of WT EGFR effects.

## 4 STUDY OBJECTIVES AND ENDPOINTS

The objectives and corresponding endpoints of the study are as follows:

# 4.1 Objectives

# 4.1.1 Primary Objective

 To compare the antitumor efficacy of oral single-agent CO-1686 with that of erlotinib as measured by PFS, when administered as a first-line targeted treatment to patients with EGFR-mutated, advanced/metastatic NSCLC

# 4.1.2 Secondary Objectives

- To compare secondary measures of clinical efficacy (ORR, DR, and OS) of oral single-agent CO-1686 with that of erlotinib when administered as a first-line targeted treatment in patients with advanced/metastatic NSCLC whose tumors have EGFR-activating mutations
- To assess PFS, ORR, DR, and OS in patients with baseline T790M mutations based on central allele-specific polymerase chain reaction (PCR) EGFR mutation assay
- To assess quality of life (QOL) using the patient-reported outcomes (PRO) of European Organization for Research and Treatment of Cancer Core Quality of Life Questionnaire (EORTC QLQ-C30) and the EORTC Quality of Life Questionnaire Lung Cancer module (EORTC QLQ-LC13), 15 the Dermatology Life Quality Index (DLQI), 16 and the EQ-5D instrument 17 in patients receiving treatment with CO-1686 versus erlotinib
- To evaluate safety and tolerability of CO-1686 versus erlotinib in patients with advanced/metastatic NSCLC whose tumors have EGFR-activating mutations
- To determine PK of CO-1686 in this patient population using population PK (POPPK) methods and explore correlations between PK, exposure, response, and/or safety findings

# 4.1.3 Exploratory Objectives

- To compare DCR of oral single-agent CO-1686 with that of erlotinib when administered as a first-line targeted treatment in patients with advanced/metastatic NSCLC whose tumors have EGFR-activating mutations
- To assess DCR in patients with baseline T790M mutations based on central allele-specific PCR EGFR mutation assay
- To compare kinetics of tumor growth between treatment arms measured by rate of change in sum of the longest diameters of target lesions (SLD) or rate of change of estimated or measured assessments of tumor volume
- To compare efficacy between treatment arms in patients with baseline T790M+ disease, detected using an ultra-sensitive research assay
- To compare the effect between treatment arms in patients who develop progressive disease (PD) while on study treatment but continue to receive assigned study treatment with CO-1686 or erlotinib beyond progression

- To evaluate concordance of EGFR mutation detection between patient tissue and plasma and to assess CO-1686 or erlotinib mediated alterations in levels of EGFR mutation detected using circulating tumor DNA (ctDNA) obtained from patient plasma
- To explore tissue and blood-based biomarkers that may be predictive of response or primary resistance to CO-1686 or erlotinib and investigate mechanisms of acquired resistance to treatment with CO-1686 or erlotinib using patient tumor tissue and blood samples

# 4.2 Endpoints

# 4.2.1 Primary Endpoints

• PFS according to RECIST Version 1.1 as determined by investigator review (invPFS)

# 4.2.2 Secondary Endpoints

- ORR, and DR, according to RECIST Version 1.1 as determined by investigator review, and OS
- invPFS, ORR, DR, and OS in patients with baseline T790M mutations confirmed by central EGFR mutation assay
- Change from baseline in QOL as measured using the PRO of EORTC QLQ-C30, EORTC QLQ-LC13, the DLQI, and the EQ-5D following treatment with CO-1686 versus erlotinib
- Treatment-emergent AEs, laboratory abnormalities and ECG abnormalities
- Plasma PK parameters for CO-1686 based on sparse sampling

## 4.2.3 Exploratory Endpoints

- DCR according to RECIST Version 1.1 as determined by investigator review
- DCR in patients with baseline T790M mutations confirmed by central EGFR mutation assay
- Rate of change in SLD
- Rate of change in tumor volume (measured or modeled)
- InvPFS, ORR, DR, DCR, time-to-treatment failure, and OS in patients who develop PD while on study treatment but continue to receive assigned study treatment with CO-1686 or erlotinib beyond progression
- Concordance of tumor and plasma ctDNA mutational analysis using contemporaneous samples
- Time from randomization to second observed increase over nadir in plasma mutant EGFR ctDNA levels (activating mutation, T790M mutation, either or both)
- Fraction of patients exhibiting disappearance of mutant EGFR ctDNA after initiating treatment with CO-1686
- Change from baseline in other tissue and blood biomarkers associated with the EGFR signaling pathways and relationship with clinical efficacy outcomes

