#### 11.2.4.1 Primary Endpoint

The primary endpoint of the study is invPFS.

invPFS will be calculated as 1+ the number of days from the date of randomization to disease progression, as determined by the investigator or death due to any cause, whichever occurs first. Patients without a documented event of progression will be censored on the date of their last adequate tumor assessment (i.e., radiologic assessment) or date of randomization if no tumor assessments have been performed.

Kaplan-Meier methodology will be used to summarize invPFS. The stratified logrank and the HR will be used for comparing the invPFS distributions among the CO-1686 and erlotinib-treated patients. The invPFS analysis will be stratified by EGFR mutation status (L858R, exon 19 deletion, or other) and territory of residence at time of randomization (Asia vs non-Asia). If the exon 19 deletion subgroup or other mutation subgroup has fewer than 30 patients than these subgroups will be combined for this analysis.

A PFS sensitivity analysis based on an independent radiographic review (irrPFS) will be performed. The irrPFS is defined as the time from randomization to disease progression according to RECIST v1.1 as assessed by independent radiographic review, or death due to any cause, whichever occurs first.

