## 11.2.4.2 Secondary Efficacy Endpoints

#### **OBJECTIVE RESPONSE RATE**

The ORR is the proportion of patients with a best overall response of partial response (PR) or CR recorded from the start of the treatment until disease progression or recurrence. The frequency and percentages of patients with a best overall response of CR, PR, stable disease (SD), or progressive disease (PD) will also be summarized.

The frequency of patients with CR or PR will be compared between treatment groups using the Fisher's Exact Test.

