## **DURATION OF RESPONSE**

The DR for CR and PR will be measured from the date that any of these best responses is first recorded until the first date that PD is objectively documented. DR will be summarized using descriptive statistics (N, mean, standard deviation, median, minimum, and maximum) as well as categorically. For patients who continue treatment post-progression, the first date of progression will be used for the analysis.

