#### 11.2.6 Exploratory Analyses

#### 11.2.6.1 Disease Control Rate

The DCR is the percentage of patients with a CR, PR, or SD lasting at least 12 weeks. The frequency and percentages of patients with a best overall response of CR, PR, SD lasting at least 12 weeks, SD lasting less than 12 weeks, or PD will be summarized.

The frequency of patients with CR, PR, SD for > 12 weeks will be compared between treatment groups using the Fisher's Exact Test.

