#### 11.2.6.3 Tissue and Blood Biomarkers

The change from baseline in tissue and blood biomarkers associated with the EGFR signaling pathway will be summarized with descriptive statistics and the t-test will be used to compare the mean changes between CO-1686 and erlotinib at each scheduled visit.

Both the time from randomization to the first observed increase in plasma mutant EGFR levels and the time from first observed increase in plasma mutant EGFR levels to disease progression will be summarized using Kaplan-Meier methodology.

11.2.6.4 Phase 2 Part Only: Subgroup of Patients that Crossover to CO-1686 from Erlotinib

The subgroup of patients that are initially randomized to erlotinib, experience a RECIST radiographic event of disease progression and test positive for the T790M mutation will be allowed to continue in the study after the initial event of disease progression and crossover to treatment with CO-1686.

The efficacy and safety of CO-1686 will be summarized descriptively in this subgroup of patients (treatment-emergent AEs, invPFS, ORR, DR, DCR and OS).

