### **Evaluation of Best Overall Response**

The best overall response is the best response recorded from the start of the treatment until disease progression/recurrence (taking as reference for PD the smallest measurements recorded since the treatment started). The patient's best response assignment will depend on the achievement of both measurement and confirmation criteria.

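### Four of the six exploratory endpoints for patients treated beyond progression stop at first progression, so a first-line PFS difference can be mistaken for a post-progression effect

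*Combined protocol and SAP*

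**What the plan says.** Section 4.1.3 sets this exploratory objective: "To compare the effect between treatment arms in patients who develop progressive disease (PD) while on study treatment" and who stay on their assigned drug. Section 4.2.3 attaches six endpoints to it: "InvPFS, ORR, DR, DCR, time-to-treatment failure, and OS in patients who develop PD while on study treatment but continue to receive assigned study treatment".

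The definitions are elsewhere in the document:

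- **invPFS** (11.2.4.1): "invPFS will be calculated as 1+ the number of days from the date of randomization to disease progression", or to death if that comes first.
- **ORR** (11.2.4.2): best response "recorded from the start of the treatment until disease progression or recurrence". Appendix A agrees: "The best overall response is the best response recorded from the start of the treatment until disease progression/recurrence".
- **DR** (11.2.4.2): the clock stops at first PD, and the text addresses these patients directly: "For patients who continue treatment post-progression, the first date of progression will be used for the analysis".
- **DCR** (11.2.6.1): "The DCR is the percentage of patients with a CR, PR, or SD lasting at least 12 weeks". Appendix A measures stable disease from treatment start until the progression criteria are met.
- **OS** (11.2.4.2): from first dose to death.
- **Time-to-treatment failure**: not defined anywhere.

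Section 11.2.6 contains no analysis for this subset. For the separate Phase 2 crossover subgroup, 11.2.6.4 says: "The efficacy and safety of CO-1686 will be summarized descriptively in this subgroup of patients (treatment-emergent AEs, invPFS, ORR, DR, DCR and OS"). It gives no time origin.

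**The concern.** The question is whether continuing one drug past progression does more than continuing the other. Four of the six endpoints are already fixed when the first post-progression dose is taken. OS contains the period of interest but adds to it the whole time to progression, which the trial expects to differ between arms. A reader shown these endpoints under this heading could take a first-line difference as support for treating past progression with one drug, an option that Appendix D still offers.

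The subset is also not a randomized comparison. Under Section 5.1.2, entry needs progression, further patient consent, the investigator's judgement and sponsor approval. Before Amendment 3, a Phase 2 erlotinib patient with T790M at progression could instead cross over to CO-1686 (Section 9.3). CO-1686 progressors had no counterpart to that route.

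**Working it through.** **1. Where each clock starts and stops**

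| Endpoint | Starts | Stops | Post-progression information |
|---|---|---|---|
| invPFS | Randomization | First PD or death | None |
| ORR | Treatment start | First PD | None |
| DR | First response | First PD (explicit) | None |
| DCR | Treatment start | First PD | None |
| OS | First dose | Death | Yes, mixed with pre-PD time |
| Time-to-treatment failure | Not stated | Not stated | Cannot be determined |

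**2. The plan's own figures.** Section 11.3 gives median PFS of 10 months (erlotinib) and 13 months (CO-1686), HR about 0.80, and 640 events for about 80% power at one-sided 0.025. Schoenfeld's formula gives 4(1.960 + 0.842)² / (ln 0.80)² = 631 events. Power at 640 events is Φ(√640/2 × 0.2231 − 1.960) = Φ(0.863) = 80.6%. The figure reproduces. The medians themselves imply 10/13 = 0.769. No figure is given for the post-progression subset.

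**3. A null post-progression effect.** From the documents: exponential PFS with medians 13 and 10 months. Assumed: exponential post-progression survival, identical in both arms, with median 8, 12 or 18 months; every member progresses; no censoring; no selection by prognosis. OS is the sum of the two times. With a = ln 2 / PFS median and b = ln 2 / post-progression median, S(t) = (b·e^(−at) − a·e^(−bt)) / (b − a). Solving S(t) = 0.5:

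| Post-PD median (assumed) | Median OS, CO-1686 vs erlotinib | Cox HR, OS from start | Cox HR, survival from first PD |
|---|---|---|---|
| 8 months | 25.1 vs 21.7 | 0.80–0.81 | about 1.0 |
| 12 months | 30.3 vs 26.6 | 0.83 | about 1.0 |
| 18 months | 37.3 vs 33.3 | 0.87–0.88 | about 1.0 |

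The HRs come from simulation; the ranges are the spread between runs of different size.

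**4. How often the null is rejected.** Same model, 2,000 simulated trials per scenario, one-sided logrank at 0.025. The number of continuers per arm is assumed. For time-to-treatment failure, an origin at randomization and a median of 4 months on drug after PD are also assumed.

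| Continuers per arm | invPFS | OS from start | Time-to-treatment failure (assumed origin) | Survival from first PD |
|---|---|---|---|---|
| 50 | 25–27% | 11–19% | 23–26% | 2–3% |
| 100 | 44–46% | 16–31% | 42–44% | 2–3% |
| 200 | 75% | 29–58% | 72–73% | 2–3% |

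With equal PFS in the two arms (10 months each, 100 per arm, post-PD median 12 months), every HR is about 1.00 and rejection is about 2–3%. The signal therefore comes wholly from the period before progression.

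**5. Selection, with the clock restarted at PD.** Assume 55% of progressors are T790M-positive (the synopsis gives 50% to 60%), all such erlotinib patients leave by crossover, and no drug effect exists. If the post-progression survival median of T790M-positive patients is 0.67, 1.0, 1.25 or 1.5 times that of the others, the HR from PD is 1.22, 1.00, 0.88 or 0.79. The assumption that all leave is an upper bound, because Section 9.3 also applies laboratory, QT and cardiac criteria and sponsor approval. It concerns Phase 2 only.

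**The case against.** The strongest reply is that the impact is small and parts of the problem are already handled. Much of this stands.

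- **Exploratory only.** This is one bullet among nine exploratory endpoints, with no decision rule attached. Development in NSCLC has stopped and no more patients will be enrolled. This limits severity but does not make the endpoints fit the objective.
- **None of the six endpoints can see post-progression treatment.** A reader might infer this, but it goes too far. OS does include that period. Time-to-treatment failure may also, depending on where it stops; that it starts before PD is the usual reading, not a stated one.
- **Crossover invPFS describes erlotinib.** A reader might infer this because every member already has an invPFS event. The documents do not support it: Section 9.3.1 and the Table 9-2 scan footnote make the scan showing progression on erlotinib the crossover baseline, and 11.2.6.4 says that the summary concerns CO-1686. Only the time origin is missing.
- **Timing from PD gives a fair comparison.** It does not. Step 5 shows HRs from 0.79 to 1.22 with no drug effect.
- **All the data are in hand.** Not fully. Section 9.6.2.1 required post-PD scans until the patient left the study, but Appendix D leaves them to the treating physician and ends participation after the End-of-Treatment visit.

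One might also argue that re-baselining at PD was intended for treatment beyond progression. No passage says so, and the DR rule says the opposite.

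**Conclusion.** The point holds in a limited form. As defined, invPFS, ORR, DR and DCR cannot inform the post-progression objective, OS is diluted by pre-progression time, and time-to-treatment failure is undefined. Under the design PFS medians and no post-progression effect, OS from the start gives an HR of about 0.80 to 0.88 where the value from PD is about 1.0. These sizes rest on exponential times, assumed post-progression medians of 8 to 18 months, and no censoring or selection. The direction does not depend on the assumed medians, but it does need unequal PFS; selection that differs by arm can add a bias of its own, in either direction. Severity is low. The primary invPFS analysis, its power and the interim analyses are unaffected.

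**What to change.** **In 4.1.3, 4.2.3 and Section 11**

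- Time the endpoints for this subset from first PD: time to discontinuation of assigned treatment, survival and, where post-PD scans exist, further progression measured against the scan at first PD. Flag lesions given local treatment, which Section 8.1.1 allows after progression and which would disturb the new reference.
- Define the start and stop of time-to-treatment failure.
- Present the results descriptively by arm, with the number and characteristics of continuers, and state that restarting the clock does not remove selection.
- Name the data cut, since scans and survival follow-up may be incomplete for patients ongoing under Amendment 3.

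**In 11.2.6.4**, state XO-C1D1 as the time origin. The baseline scan needs no change.

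**Cost.** The changes are to wording only. The comparison between arms becomes descriptive, and scan-based results may be incomplete for patients ongoing under Amendment 3.
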